### ***Recruitment***

The target enrollment is 50 participants in accordance with published guidance for pilot studies and to allow for drop-outs. We partnered with two different entities for participant recruitment, using different strategies. The first is a private, non-profit health system that operates Federally qualified community health centers in North Carolina that also administer WIC benefits. During WIC encounters, WIC nutritionists (n=2) will upload the name, phone number and email address of WIC beneficiaries who are interested in joining the pilot into a secure online Duke Box folder. Research assistants will upload this information into REDCap (Research Electronic Data Capture), a secure, web-based software platform designed to support data capture and management for research studies. The second recruitment entity is the WIC office from the 2nd most populated county in North Carolina. This county WIC office will include flyers in mailings sent to all new WIC recipients. These flyers will provide information about the pilot study and will include a QR code that caregivers can scan to take them directly to the screener.

Additionally, the Nutrition Services Branch within the North Carolina Division of Public Health, which implements the WIC program for North Carolina, will alert all WIC directors in the state of the pilot study via email. The email will include the flyer with the QR code for WIC directors to distribute throughout their WIC clinics as they see fit. We will also utilize social media platforms, such as Facebook, and Duke University websites to distribute information about the study and aid in recruitment. Interested caregivers can also find a link to the screener from a study-specific website, <https://healthyrootsstudy.com>. This website contains study and contact information for the research team.

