### ***Analytic Approach***

#### ***Primary Outcomes***

*Implementation* will be assessed through intervention engagement calculated by dividing the number of days with valid tracking data (numerator) over the total number of possible tracking days (denominator). We will calculate and compare engagement rates by week. We will create a dichotomous outcome variable comparing high vs. low engagers using an established cutoff of 80% or more engagement in weekly self-monitoring . Bivariate analyses using *t* tests and chi-square will be used to examine predictors of intervention engagement. Poisson regression with a robust variance will be used to examine sociodemographic differences among those with higher levels of engagement (80% or more weeks of tracking) and estimate risk ratios and 95% confidence intervals.

*Preliminary efficacy* will be measured by assessing changes in diet quality. Dietary intake will be measured using the ASA24 recall tool. Participants will be asked via email to complete 2 separate dietary recalls (1 week and 1 weekend day) within a 14-day period prior to enrollment and again upon study completion, for a total of 4 dietary recalls. These data will be used to calculate a Healthy Eating Index-2015 (HEI) score, which consists of 13 components, 9 of which assess adequacy of the diet, including 1) total fruit; 2) whole fruit; 3) total vegetables; 4) greens and beans (including peas); 5) whole grains; 6) dairy; 7) total protein foods; 8) seafood and plant proteins; and 9) fatty acids, which is a ratio of poly- and mono- unsaturated to saturated fatty acids. The remaining 4 assess dietary components recommended to be consumed in moderation: 10) refined grains; 11) sodium; 12) added sugars; and 13) saturated fats . For all components, higher scores reflect better diet quality as moderation components are reverse scored. Each component is scored on a density basis rather than absolute scores, either as a percentage of calories or per 1000 calories allowing use of the HEI for a range of ages and populations. Summed scores of the 13 components yield a maximum total score of 100, with a higher score reflecting greater compliance with the 2015–2020 Dietary Guidelines for Americans .

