#### ***Analysis***

Data from this pilot study will be descriptive with outcomes being estimates of variables relating to feasibility . Sample characteristics will be described as frequencies for categorical variables and means for continuous variables. HEI-2015 scores will be summarized as means and standard deviations and percent maximum score [(mean score/maximum score) x 100%]. We will explore intervention effects on change in HEI score from baseline to 12 weeks using a two-sample *t*-test. Although we will likely not have enough power, we will conduct exploratory analyses to assess differences in HEI scores among low vs. high engagers using linear regression. Similar analysis will be conducted for changes in relevant behavioral and psychosocial variables.

If the distribution of any outcome is heavily skewed, we will either appropriately transform the data so it's normally distributed or use a generalized linear mixed model with an appropriate link function. Sensitivity analyses will fit linear mixed models with a full maximum likelihood estimation using all available data to allow for responses to be missing at random, where the missing mechanism may be related to either observed covariates or response variables, but not related to the unobserved data. All analyses will be conducted using STATA 14 (StataCorp, College Station, TX).

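### The sensitivity mixed models use full maximum likelihood and name no small-sample reference distribution, so their intervals come out slightly too narrow; REML with small-sample degrees of freedom is a one-phrase fix

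*SAP*

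**What the plan says.** The SAP, under Analysis, sets out the check on missing responses: "Sensitivity analyses will fit linear mixed models with a full maximum likelihood estimation using all available data". The purpose given in the same sentence is "to allow for responses to be missing at random". No small-sample degrees-of-freedom method is named, and nothing says whether intervals use a normal or a *t* quantile.

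The outcome these models would check is the "change in HEI score from baseline to 12 weeks". The same section also plans exploratory work to "assess differences in HEI scores among low vs. high engagers using linear regression".

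On size, the Recruitment section of the protocol says: "The target enrollment is 50 participants in accordance with published guidance for pilot studies and to allow for drop-outs". No dropout rate follows. On purpose, the SAP says: "Data from this pilot study will be descriptive with outcomes being estimates of variables relating to feasibility".

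**The concern.** ML estimates a variance as though the fixed effects were known. REML divides by what is left after estimating them. The difference vanishes in large samples but not entirely with 30 to 50 participants, and it always runs the same way: ML standard errors are too small. If the interval is then built with 1.96 instead of a *t* quantile, a second shortfall in the same direction is added.

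The stake is modest. These models are the only part of the SAP that addresses missing responses, and they check the HEI result, which the SAP lists under Primary Outcomes as preliminary efficacy. In a pilot whose product is estimates, the interval widths should be right. A check whose intervals are slightly too narrow is slightly less reassuring when it agrees with the main analysis.

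**Working it through.** The plan gives no alpha, SD, effect size or power for these models, so there is no figure of its own to reproduce. The check is on the method.

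**Inputs**
- Enrolment: 50 (protocol, Recruitment).
- Complete pairs: 50, 40 or 30. This is an assumption covering 0% to 40% dropout, because the protocol gives no rate.
- Time points: baseline and 12 weeks, with one HEI score per participant at each (assumed; two recalls feed each score).
- Level: two-sided 95%. The SAP states 95% only for the risk ratios (Primary Outcomes); it is assumed here.
- *p*, the number of fixed effects that govern the change: 1 for the mean change, 2 for low against high engagers. The SAP names linear regression for the engager contrast; I assume the mixed model would refit it.

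**Formulas** (complete, balanced pre/post data)
1. Standard error ratio: *s* = SE(ML)/SE(REML) = √((n − p)/n).
2. Quantile ratio, if a normal reference is used: 1.96 / t(0.975, n − p).
3. Shortfall in width: 1 − *s* for ML alone (*t* quantile kept); 1 − *s* × quantile ratio for ML plus normal.
4. True error: 2 × P(t with n − p df > *q*), where *q* = *s* × t(0.975, n − p) for ML alone and *q* = 1.96 × *s* for ML plus normal.

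**Worked case, n = 50, p = 1.** *s* = √(49/50) = 0.9899, so ML alone is 1.0% too narrow. The quantile ratio is 0.9753. The product is 0.9655, so ML plus normal is 3.4% too narrow. With *q* = 1.96 × 0.9899 = 1.940 on 49 df, the true error is 5.8%.

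| Contrast | n | *s* | ML alone: too narrow by | Error | Quantile ratio | ML + normal: too narrow by | Error |
|---|---|---|---|---|---|---|---|
| Mean change (p = 1) | 50 | 0.9899 | 1.0% | 5.2% | 0.9753 | 3.4% | 5.8% |
| | 40 | 0.9874 | 1.3% | 5.3% | 0.9690 | 4.3% | 6.0% |
| | 30 | 0.9832 | 1.7% | 5.4% | 0.9583 | 5.8% | 6.4% |
| Low vs high engagers (p = 2) | 50 | 0.9798 | 2.0% | 5.5% | 0.9748 | 4.5% | 6.1% |
| | 40 | 0.9747 | 2.5% | 5.6% | 0.9682 | 5.6% | 6.4% |
| | 30 | 0.9661 | 3.4% | 5.8% | 0.9568 | 7.6% | 6.9% |

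**REML without the degrees of freedom.** REML with a normal quantile, p = 1, still has a true error of 5.6%, 5.7% and 6.0% at n = 50, 40 and 30. Both parts of the correction are needed if the reference is normal.

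**Check by fitting.** Random-intercept models were fitted by ML and by REML to simulated data (assumed SD 12, correlation 0.5, dropout depending on the baseline score). The ratio of ML-plus-normal width to REML-plus-*t* width was 0.966 with complete data, 0.956 with about 39 completers and 0.943 with about 29, in line with the formulas. The runs (300 and 1,000 data sets) are too few to judge coverage to a fraction of a point: the Monte Carlo standard error near 95% is √(0.95 × 0.05/1000) = 0.7 points, or 1.3 points with 300. The error rates above therefore rest on the formulas.

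**The case against.** The strongest reply is that the sentence is about missing data, not variance estimation. It keeps participants without 12-week recalls in the analysis under a missing-at-random assumption, and ML does that validly. The main question for such a check is whether the estimate moves when incomplete cases are included, and ML and REML give nearly the same point estimate. The SAP sets no alpha, decision rule or success threshold for these models, and the pilot is declared descriptive. Full ML with about 50 participants is a legitimate prespecified choice and contradicts nothing in the documents. All of this stands, and it limits the point to a minor one. It does not make ML preferable: REML uses the same data under the same assumption.

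A reader might infer that full ML by itself makes the intervals 3% to 8% too narrow. The documents do not support that. For the mean change most of the combined shortfall comes from the normal quantile, and for the engager contrast slightly more than half does; the SAP never states that quantile. What follows from the SAP's stated choice alone is 1.0% to 1.7%, or 2.0% to 3.4% for the engager contrast.

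It could also be said that the same section has a larger problem: it names a two-sample *t*-test for change from baseline, although the documents describe one group measured twice. That is a separate matter, and changing the estimation method does not touch it.

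**Conclusion.** The point holds as a small precision issue. With 30 to 50 complete pairs, ML alone gives a true error of 5.2% to 5.4% for the mean HEI change and 5.5% to 5.8% for low against high engagers, at a nominal 5%. With a normal quantile as well, these become 5.8% to 6.4% and 6.1% to 6.9%. The direction does not depend on the quantile; the size does.

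The figures assume the dropout range, one HEI score per time point, complete balanced data and a two-sided 95% level. Fixed effects beyond those counted here would enlarge the shortfall: with p = 5 and n = 40 it is 6.5% for ML alone and 9.7% with a normal quantile.

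It would be wrong to conclude that the sensitivity analysis is invalid or that the HEI estimate is biased. Coverage stays at about 93% to 95% for the two contrasts, and no stated decision depends on it.

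**What to change.** In the sensitivity-analysis sentence of the SAP, replace *full maximum likelihood estimation* with *restricted maximum likelihood (REML) estimation with Kenward-Roger or Satterthwaite degrees of freedom*, choosing one of the two. Keep the all-available-data and missing-at-random wording as it is. Naming the degrees of freedom also settles the unstated reference distribution.

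The correction is exact for complete balanced data and approximate with dropout, which is when this analysis is most useful.

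The cost is one phrase, with no further data or analyses. For the mean change, intervals widen by 1.0% (1/0.9899) at n = 50 to 1.7% (1/0.9832) at n = 30 if a *t* quantile was intended anyway. If a normal quantile was intended, they widen by 3.6% (1/0.9655) to 6.1% (1/0.9422). REML likelihoods cannot be used to compare models with different fixed effects, but the SAP plans no such comparison.
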